7.7.4 Vital Signs

The following vital signs will be collected from subjects in seated or semi-recumbent position.

- systolic and diastolic blood pressure (mmHg);
- heart rate (bpm);
- respiration rate (breaths/min);
- oral/ intra-aural body temperature (°C).

Descriptive summaries by treatment and visit will be presented for the mean of triplicate measures (rounded to the nearest integer) at Baseline, Week 12 Week 24, Week 48, and Week 96, and for single measurements collected at all other visits. The summary at each visit will pool assessments in seated or semi-recumbent positions. Vital signs data and changes from baseline will be summarized by visit using standard descriptive statistics for the Safety population. Baseline for each vital sign is the pre-dose measurement on Baseline visit (Day 1) with exceptions as defined in Section 7.1.1. For post-baseline, only data from scheduled visits will be included in the summary tables.

7.7.5 Electrocardiograms

The following quantitative ECG measurements will be recorded on the eCRF:

- heart rate (bpm)
- QRS (msec);
- RR (msec);
- PR (msec);
- QT (msec);
- Fridericia corrected QT (QTcF) interval (msec).

CONFIDENTIAL

Statistical Analysis Plan

Sponsor Name: Akero Therapeutics, Inc.
Sponsor Protocol ID: AK-US-001-0102

An overall Investigator assessment of ECG will be provided (categories "normal", "abnormal, not clinically significant" and "abnormal, clinically significant").

The ECG measurements and changes from baseline in ECG will be listed and summarized by treatment group and visit using standard descriptive statistics for the Safety Set.

The Investigator assessment will be listed and the number and percentage of subjects within each assessment category will be tabulated by treatment group and visit for the Safety Set.

Baseline for each ECG measurement is the pre-dose measurement on Baseline visit (Day 1) with exceptions as defined in Section 7.1.1. For post-baseline, only data from scheduled visits will be included in the by visit summary tables.

The number and percentage of subjects with absolute QTcF interval values in the pre-specified categories (>450, >480, and >500 msec), and QTcF interval change (>30 and >60 msec) will be summarized. The summary of maximum post-baseline QTcF will include scheduled and unscheduled visits.

7.7.6 Other safety assessments

7.7.6.1 Physical examination

Clinically relevant physical exam findings prior to the first dose of study drug will be recorded on the medical history eCRF and clinically significant findings after the first dose of study drug will be recorded as AEs.

7.7.6.2 DXA scan measurements

DXA scan measurements will include bone mineral density of the lumbar spine and femoral neck. An MMRM model with baseline covariate will be used to evaluate the changes from baseline in DXA scan measurements between the EFX arms and the placebo arm at Week 48 and Week 96, controlling for stratification factors. Least square (LS) means, 95% CIs, and p-values will be presented. The analysis will be performed using the Safety Set.

Summaries and boxplots will be presented for actual values and changes from baseline in DXA scan measurements at the collection time points defined in the Schedule of Assessments by treatment group.

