generally reversible or exhibited a trend towards reversibility in both species. The no adverse effect level (NOAEL) in both rat studies was 100 mg/kg; in the 26-week study, associated C_{max} values at the NOAEL were approximately 9 to 19-fold the modeled C_{max} in humans at 50 mg, and corresponding AUC_{0-96h} values were approximately 20 to 41-fold higher than the modeled AUC_{0-168h} in humans at 50 mg. The NOAEL in the 16-week monkey study was 30 mg/kg/dose. The NOAEL in the 26-week monkey study was 30 mg/kg in females, and not identified in males due to overall inhibition of growth with resulting deficit in bone growth and consolidation. In the 26-week monkey study, the C_{max} value at the NOAEL was 27-fold higher than the modeled C_{max} in humans at 50 mg, and corresponding AUC_{0-96h} values was 11-fold higher than the modeled AUC_{0-168h} in humans at 50 mg. The exposure multiples based on AUC values are considered conservative based on values calculated through 96 hours post-dose in animals compared to modeled values through 168 hours post-dose in humans.

Genotoxicity or carcinogenicity studies have not been conducted to date with EFX. A 2-year rat carcinogenicity study will be conducted in parallel with this program. However, studies have been conducted to examine the potential of EFX to impact cell proliferation and mitogenicity. Results of *in vitro* and short-term *in vivo* studies demonstrated that EFX was not a direct-acting mitogen and was not associated with persistent cell proliferation in liver. Moreover, staining of the liver with Ki67, a marker of active cell proliferation, showed no changes after 26 weeks of repeat-dosing of rats once weekly at up to 100 mg/kg. In addition, there were no pre-neoplastic histopathology changes observed in rats or in monkeys administered weekly subcutaneous doses up to 100 mg/kg/dose for 26 weeks. These data suggest that EFX would have minimal risk for carcinogenicity.

In fertility and early embryonic development studies in rats, EFX administration to females prior to and during mating did not impair fertility or numbers of embryos at doses up to 30 mg/kg/dose, nor did it impair fertility of males at doses up to 100 mg/kg/dose. In embryofetal development studies in rats and rabbits administered EFX every 3 days during gestation, no maternal toxicity was observed up to 100 mg/kg/dose and no embryofetal toxicity occurred at doses up to 30 mg/kg/dose. EFX was not teratogenic in rats or rabbits.

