6.10. DXA Scan

A DXA scan should include lumbar spine, femoral neck, and total hip with subjects in the standard (supine) position.

Rescreening: If a subject is rescreened with Medical Monitor approval, qualifying DXA scan results from the subject's initial screening do not need to be resubmitted for analysis to the blinded central reader if the scan is obtained \leq 6 months prior to randomization.

Please refer to the Imaging Manual for DXA imaging guidelines.

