7.1.2. Safety Endpoints

The safety endpoint is safety and tolerability of EFX in subjects with NASH.

Safety analyses include: summaries of extent of exposure, AEs, clinical laboratory tests, endogenous FGF21, ECG, BMD, vital sign assessments, body weight, anti-drug antibody (ADA) and neutralizing antibody (NAB) assessments, and concomitant medication usage.

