7.1 General Principles

All data processing, summarization and analyses will be performed using Fortrea's SAS Environment / Version 9.4 (or later) of the SAS® statistical software package.

The following principles will be applied to all tables, figures, and listings (TFLs) unless otherwise stated:

Principle	Value
Significant tests	Two-sided and use a 5% significance level for main effects and 10% significance level for interaction terms.
Treatment group labels and order presented	Placebo EFX 28 mg EFX 50 mg All EFX (as applicable) Total (as applicable)
Tables	Data in summary tables presented by assessment or parameter, treatment group, and visit (where applicable).
Listings	All individual subject data will be listed as measured and presented by treatment group, subject, and visit (where applicable), unless otherwise specified.
Descriptive summary statistics for continuous variables	Number of non-missing values (n), arithmetic mean, arithmetic standard deviation (SD), median and range (minimum and maximum). Descriptive statistics for certain continuous data will include geometric mean and geometric coefficient of variation. PK concentrations will be summarized with the set of continuous parameters including geometric mean and will add the statistic of number of samples below the limit of quantification (BLQ).
Descriptive summary statistics for categorical variables	Frequency counts and percentages [n (%)].
Denominator for percentages	Number of subjects in the analysis set, unless stated otherwise in table shell.
Include "Missing" as category	Demographics and Other Baseline Characteristics only.

Statistical Analysis Plan

Sponsor Name: Akero Therapeutics, Inc.
Sponsor Protocol ID: AK-US-001-0102

Principle	Value
Display for 0 percentages	Blank
Display collected value	Minimum and maximum
Display 1 decimal place	Q1 (25 th Percentile), Q3 (25 th Percentile), Mean, Mean Difference, Median, Standard Deviation, and Confidence Interval for all parameters except DXA parameters.
Display 3 decimal places	Q1 (25 th Percentile), Q3 (25 th Percentile), Mean, Mean Difference, Median, Standard Deviation, and Confidence Interval for DXA parameters; p-value.
Limit of precision for displays	1 decimal place, unless otherwise specified.
Date Format	DDMMYYYY

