7.1.1 Definition of Baseline

For all variables except lipids, liver enzymes variables, and blood pressure, pre-dose measurements on Baseline visit (Day 1) will be considered the baseline values. If the measurement at this visit is not available, the last available measurement (including unscheduled visit) prior to the first dose of study drug may be used as the baseline value unless it is stated otherwise. The scheduled baseline visit for FibroScan, liver biopsy, MRI-PDFF, and DXA scan is Screening.

Baseline lipid variables including Total Cholesterol, HDL-C, LDL-C, Triglycerides, non-HDL-C, VLDL-C, VLDL-T, HDL-P, IDL-P, LDL-P, VLDL-T-P, HDL particle size, LDL particle size, VLDL particle size, Lp (a), and lipoprotein insulin resistance will be the average of Screening and Baseline visit (Day 1) values. If one is missing, the available one will be used.

Baseline liver enzymes variables including ALT, AST and ALP will be the average of Pre-Baseline and Baseline visit (Day 1) values. If one is missing, the available one will be used. If both are missing, the available Screening value will be used.

Baseline blood pressure will be the average of Screening, Pre-Baseline, and Baseline visit (Day 1) values. If one value is missing, the average of the two available values will be used. If two values are missing, the available one will be used.

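### The protocol plans DXA at the total hip, but the SAP specifies no model, summary or plot for that site and gives no reason

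*SAP*

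**What the plan says.** Protocol 6.10 sets the acquisition: "A DXA scan should include lumbar spine, femoral neck, and total hip with subjects in the standard (supine) position". It refers to an Imaging Manual for the technical detail. The schedules in Protocol Appendices A and B place DXA at Screening, Week 48 and Week 96, with none at Early Termination.

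SAP 7.7.6.2 sets the analysis: "DXA scan measurements will include bone mineral density of the lumbar spine and femoral neck". It then specifies an MMRM with baseline as covariate, comparing changes "between the EFX arms and the placebo arm at Week 48 and Week 96, controlling for stratification factors", in the Safety Set, with LS means, 95% CIs and p-values. It also calls for summaries and boxplots of the DXA measurements. Baseline is fixed in SAP 7.1.1: "The scheduled baseline visit for FibroScan, liver biopsy, MRI-PDFF, and DXA scan is Screening".

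Protocol 7.1.2 names BMD among the safety analyses without restricting the site: "Safety analyses include: summaries of extent of exposure, AEs, clinical laboratory tests, endogenous FGF21, ECG, BMD, vital sign assessments". SAP 7.1 has a general rule for listings: "All individual subject data will be listed as measured and presented by treatment group, subject, and visit (where applicable), unless otherwise specified". SAP section 8 declares changes to the planned analysis not applicable and adds one note, about subjects staying on their randomised EFX dose.

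**The concern.** The two documents give different sets of sites. The sentence in SAP 7.7.6.2 is complete, with no sign of redaction, and it is the only place where the SAP says which sites make up the DXA measurements. A programmer working from it would build outputs for two sites.

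Bone is a stated interest of this trial. In the 26-week monkey study (Protocol 1.3), no NOAEL was identified in males because of "overall inhibition of growth with resulting deficit in bone growth and consolidation". Osteoporosis at screening is an exclusion, and P1NP and CTX-1 are measured and modelled. The animal findings are attributed to growth and body-weight effects and name no skeletal site, so they justify monitoring bone and do not point to the hip in particular.

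What is at stake is the completeness of the bone-safety report. A difference between arms at the total hip would have to be noticed by reading a listing. If total hip were added only after the spine and femoral neck results were known, the choice of sites could look selective.

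**Working it through.** There is no stated figure to reproduce. The check is a comparison of text and a count.

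**1. Sites, side by side**

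| Site | Planned (Protocol 6.10) | Named for analysis (SAP 7.7.6.2) |
|---|---|---|
| Lumbar spine | yes | yes |
| Femoral neck | yes | yes |
| Total hip | yes | no |

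Planned: 3. Named for analysis: 2. Not named: 3 − 2 = 1.

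**2. Does other SAP text restore total hip?** The remaining references to DXA or BMD are the safety variables (SAP 3.5), the BMD row of SAP Table 3, the DXA visit windows (SAP 6.1), the decimal-place rule (SAP 7.1) and the baseline definition (SAP 7.1.1). None names a site, and total hip appears nowhere in the SAP.

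**3. Is the difference explained?** No. The only note in SAP section 8 concerns the EFX dose.

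**4. What would still be reported for total hip?** Any recorded values fall under the listing rule in SAP 7.1. A listing shows values by arm, subject and visit. It gives no LS mean, between-arm difference, interval, by-visit summary or plot.

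**5. Contrasts**

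Individual-arm contrasts = sites x EFX arms compared with placebo x post-baseline visits.

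- As written: 2 x 2 x 2 = 8
- With total hip: 3 x 2 x 2 = 12
- Added: 12 − 8 = 4

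**6. Subjects**

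Protocol 5.2.2 gives 40 per arm, so the planned number is 3 x 40 = 120. This is an upper bound at Weeks 48 and 96. Subjects will drop out, anyone refusing the Week 24 biopsy is discontinued (Protocol 3.1), and no DXA is scheduled at Early Termination. The documents give no figure for how many will have scans at those visits.

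**The case against.** The strongest reply is that the SAP drops nothing it was bound to analyse. The protocol's statistical section lists BMD among the safety analyses and never commits to a total hip analysis. Screening DXA also serves the osteoporosis exclusion, so acquiring a region does not by itself oblige anyone to model it. The femoral neck is part of the hip, so the hip is not left unexamined. Spine and femoral neck BMD, the two bone-turnover markers and adverse events also cover bone safety, and no decision rule depends on total hip.

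Most of this stands, and it limits the point. Several stronger readings are tempting, and the documents do not support them:

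- **The data are thrown away.** They are not: SAP 7.1 would list any recorded values.
- **Total hip is measured in every scan.** The protocol's verb is should, and the Imaging Manual is not among these documents. Acquisition is planned, not assured.
- **BMD is a safety endpoint in its own right.** Protocol 7.1.2 makes safety and tolerability the endpoint, with BMD one item in the analyses.
- **A third of the bone information is lost.** One in three counts sites. The sites are not independent sources of information, and the femoral neck already covers part of the hip.
- **The SAP explicitly excludes total hip.** It says the measurements will include two sites and never says only. The exclusion follows because this is the sole definition of what is analysed.

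None of these explains why a site named in the protocol has no planned analysis.

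**Conclusion.** The mismatch is real and unexplained. As written, the SAP gives no between-arm estimate or interval at Week 48 or Week 96 for one of the three DXA sites the protocol plans, in at most about 120 subjects. Recorded values would appear only in listings.

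Two assumptions underlie this: that total hip BMD was acquired and delivered as a variable, and that the analysis follows SAP 7.7.6.2 literally. If the first fails, what remains is a missing explanation in section 8.

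A reader might infer that the trial's bone-safety conclusion is compromised. The documents do not support that: two sites and two bone markers are modelled, and nothing shows that adding total hip would change a conclusion. This is a safety-reporting gap worth closing because closing it costs almost nothing. The primary endpoint, sample size and alpha are unaffected.

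**What to change.** Amend the opening sentence of SAP 7.7.6.2 to name lumbar spine, femoral neck and total hip, and apply the same MMRM, summaries and boxplots to total hip. If the imaging reader did not deliver total hip BMD, state that in SAP section 8 instead.

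The cost is one phrase and one more set of tables and plots, with no new procedure for subjects. The small downside is four more safety contrasts with unadjusted p-values, to be read descriptively alongside the other two sites.

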7.7.6.3 Anti-drug antibody and neutralizing antibody

The incidence of pre-existing, treatment-emergent positive ADA, positive ADA at any time point, negative ADA at all time points, and NAb, if any, will be summarized by treatment and period.

CONFIDENTIAL

Statistical Analysis Plan

Sponsor Name: Akero Therapeutics, Inc.
Sponsor Protocol ID: AK-US-001-0102

Pre-existing ADA is defined as positive ADA result at or before dosing. Treatment-emergent positive ADA is defined as negative result at or before dosing and positive result post dose. Titers will also be summarized descriptively for positive ADAs.

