In the subjects receiving at least one dose of EFX, 41 of 57 individuals (71.9%) were positive for treatment-induced ADA, compared to none in the placebo group. While the majority of subjects developed ADA during the study, individual data from all subjects with treatment-induced ADA indicated that the measured antibody titers were low with a median observed titer value at 20 weeks of 1:8.67. In addition, only 4 subjects (7.0% of EFX-treated subjects) demonstrated emergence of fibroblast growth factor 21 (FGF21) cross-reactive antibodies. Only 1 subject was positive for neutralizing antibodies (NAb) at a single time point, and this subject subsequently tested negative for ADA.

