2.2. Secondary Objectives

The secondary objectives of this study are:

- To evaluate the effect of EFX compared to placebo on achieving NASH resolution in subjects with stage 2 or 3 fibrosis.
- To evaluate the effect of EFX compared to placebo on MRI-PDFF based on hepatic fat fraction.
- To evaluate the effect of EFX compared to placebo on non-invasive markers of fibrosis.
- To evaluate the effect of EFX compared to placebo on lipoproteins.
- To evaluate the effect of EFX compared to placebo on markers of glycemic control.
- To evaluate the effect of EFX compared to placebo on weight change.
- To assess the safety, tolerability, and immunogenicity of EFX.

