6.16. Anti-Drug Antibody and Neutralizing Antibody Sampling

Samples will be obtained for detection of anti-drug antibodies (ADA) against EFX as outlined in the Schedule of Assessments ([Appendix A - B](#)).

In the event of a positive anti-EFX antibody detection, a neutralizing ADA assay will be run for the sample timepoint with the positive result.

Subjects who test positive for binding antibodies to EFX at the final scheduled study visit will be required to return for additional follow-up testing. This testing is to occur once the site has been notified of the positive result and approximately every 3 months until: (1) antibodies are no longer detectable or (2) the subject has been followed for a period of at least 6 months (\pm 2 weeks) after administration of EFX. All follow-up results, both positive

and negative, will be communicated to the sites. More frequent testing (e.g., every month) or testing for a longer period of time may be requested in the event of safety-related concerns. Follow-up testing is not required where it is established that the subject did not receive EFX.

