7.11. Immunogenicity Analysis

The incidence of pre-existing, treatment-emergent positive ADA, positive ADA at any time point, negative ADA at all time points, and NAB, if any, will be summarized by treatment and period. Pre-existing ADA is defined as positive ADA result at or before dosing. Treatment-emergent positive ADA is defined as negative result at or before dosing and positive result post dose. Titers will also be summarized descriptively for positive ADAs.

Efficacy and safety variables may be analyzed based on the positive ADA and negative ADA subjects. Additionally, the impact of immunogenicity on PK and PD will be analyzed.

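### The treatment-emergent ADA incidence counts only negative-to-positive subjects, so it omits boosted pre-existing antibody and will be too low if any boosting occurs

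*SAP*

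**What the plan says.** Immunogenicity belongs to a stated secondary objective (Protocol 2.2): "To assess the safety, tolerability, and immunogenicity of EFX".

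The two documents define the ADA categories identically. Protocol 7.11: "Pre-existing ADA is defined as positive ADA result at or before dosing". SAP 7.7.6.3: "Treatment-emergent positive ADA is defined as negative result at or before dosing and positive result post dose". Neither has a category for a pre-existing antibody that rises on treatment, and neither sets a criterion based on titre.

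The lines to be reported, by treatment and period, are "The incidence of pre-existing, treatment-emergent positive ADA, positive ADA at any time point, negative ADA at all time points, and NAb, if any" (SAP 7.7.6.3). On titres the same section adds only this: "Titers will also be summarized descriptively for positive ADAs". Protocol 6.16 says that after a positive ADA result "a neutralizing ADA assay will be run for the sample timepoint with the positive result", whatever the subject's baseline status. SAP Table 3 assigns ADA and NAb to the Safety Set. The default denominator for percentages in SAP 7.1 is: "Number of subjects in the analysis set, unless stated otherwise in table shell".

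**The concern.** A subject who is positive before the first dose has only one possible label. If the titre stays flat, the subject is pre-existing. If it climbs steeply on drug, the subject is still pre-existing. The treatment-emergent line cannot tell the two apart, and under the default denominator such a subject dilutes the percentage without being able to enter the numerator. No planned summary uses a within-subject change in titre or a fold-rise rule.

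This departs from how the same plan treats other safety data. A laboratory value already abnormal at baseline counts as treatment-emergent if it worsens by a toxicity grade (SAP 7.7.3, Protocol 7.8.3). A condition present before treatment becomes an adverse event if its severity increases (Protocol 6.22). For ADA alone, worsening from a positive baseline does not count.

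What is at stake is the meaning of one reported incidence for a drug with frequent ADA. In Phase 2a, "41 of 57 individuals (71.9%) were positive for treatment-induced ADA, compared to none in the placebo group" (Protocol 1.4.1.2). That sentence says treatment-induced, which on its face is what the present rule measures. The label treatment-emergent suggests a broader count than the rule delivers.

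**Working it through.** **Reproducing the only ADA incidence in the documents.** Protocol 1.4.1.2 gives 41 of 57 EFX subjects: 41/57 = 0.7193, or 71.9%, as stated. The other 57 − 41 = 16 subjects (16/57 = 28.1%) were not treatment-induced. The text does not say how many of them were positive at baseline, so 28.1% is an arithmetic ceiling on boosted but uncounted subjects in Phase 2a, not an estimate.

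**Inputs for this trial.**
- n = 40 per EFX arm (Protocol 5.2.2).
- t = 41/57, the induced rate among baseline-negative subjects. This carries the Phase 2a figure over as an assumption; the shortfall does not depend on it.
- q = proportion ADA-positive before dosing. Not in the documents; assumed 0 to 20%.
- b = share of those whose titre is boosted. Not in the documents; assumed 50% or 100% for illustration, and it could be zero.

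**Formulas, with all subjects in the arm as denominator.**
- Treatment-emergent as now defined: (1 − q)t
- With boosted responses added: (1 − q)t + qb
- Positive at any time: (1 − q)t + q
- Shortfall: [(1 − q)t + qb] − (1 − q)t = qb

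**Example, q = 10% and b = 50%.** As defined: 0.90 × 0.7193 = 64.7%. Boosted part: 0.10 × 0.50 = 5.0 points. Combined: 69.7%. Positive at any time: 64.7% + 10% = 74.7%.

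| Assumed q | Assumed b | As defined | Boosted added | Shortfall (points) | Positive at any time |
|---|---|---|---|---|---|
| 0 | any | 71.9% | 71.9% | 0 | 71.9% |
| 5% (2 of 40) | 50% | 68.3% | 70.8% | 2.5 | 73.3% |
| 5% | 100% | 68.3% | 73.3% | 5.0 | 73.3% |
| 10% (4 of 40) | 50% | 64.7% | 69.7% | 5.0 | 74.7% |
| 10% | 100% | 64.7% | 74.7% | 10.0 | 74.7% |
| 20% (8 of 40) | 50% | 57.5% | 67.5% | 10.0 | 77.5% |
| 20% | 100% | 57.5% | 77.5% | 20.0 | 77.5% |

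Three things follow.
- One boosted subject is worth 1/40 = 2.5 points in an arm.
- The any-time column does not depend on b, so changing the definition leaves it untouched. It is also an upper bound on the corrected treatment-emergent rate.
- The as-defined rate falls as q rises even with no boosting, because baseline-positive subjects stay in the denominator. At q = 10% the fall is 71.9 − 64.7 = 7.2 points. Among baseline-negative subjects alone the induced rate would stay at 71.9% in every row, so the denominator needs stating separately from the boosting question.

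**The case against.** The case for leaving the definition alone is substantial, and most of it stands.

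First, the protocol and SAP agree word for word, so there is no internal contradiction.

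Second, a boosted subject is not lost from the report. The subject appears as pre-existing and as positive at any time, enters the titre summary and has the neutralizing assay run on each positive sample. SAP 7.1 and Protocol 7.2 also promise listings of all individual data, which as a general principle should let a reader see a titre rise subject by subject.

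Third, the line is descriptive. No test or procedure depends on it; the antibody follow-up in Protocol 6.16 applies to anyone positive at the final visit, treatment-emergent or not.

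Fourth, the documents give no baseline prevalence and no boosting data, and the denominator is a default that the table shells (not supplied) may override.

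Two stronger readings are tempting, and the documents support neither. A reader might infer that immunogenicity as a whole is understated. It is not: only the treatment-emergent line can be low, and only if some subject is both positive at baseline and boosted. A reader might also infer that boosted subjects would fall in the wrong group when outcomes are compared by ADA status. Protocol 7.11 frames that comparison as positive versus negative ADA, not treatment-emergent versus not, and makes it optional for efficacy and safety. A boosted subject is ADA-positive. The planned look at PK and PD is not tied to the treatment-emergent label either.

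What the objection does not answer is that the plan has no summary by arm of how many pre-existing responses rose on drug. A listing allows that count to be made afterwards, but without a threshold fixed in advance.

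**Conclusion.** The point holds in a limited form. The treatment-emergent ADA incidence omits treatment-boosted responses by definition. It will be too low by q × b, where q is baseline prevalence and b the boosted share. The documents give neither, and the shortfall may be zero. It cannot exceed q, and each boosted subject accounts for 2.5 points in an arm of 40. The table's values of q and b are illustrations only. Any-time positivity, NAb results and listings are not affected, and the comparisons by ADA status are not misclassified. This is a worthwhile small improvement to a descriptive safety line; it does not touch the efficacy conclusions.

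One related gap: a subject with no pre-dose ADA result meets neither definition, and SAP 7.7.6.3 has no rule for that case, although SAP 7.7.3 has one for laboratory grades.

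**What to change.** In SAP 7.7.6.3:
- Define treatment-emergent ADA as treatment-induced (negative before dosing, positive after) plus treatment-boosted (positive before dosing, with a post-dose titre above a set multiple of the subject's baseline titre).
- Fix the multiple from assay variability before unblinding. The documents contain nothing from which to derive it. Because SAP 7.9 has a sponsor team unblinded at the Week 24 analysis, it should be set by people who have not seen ADA results by arm.
- Report the two components separately and combined, with a denominator for each: baseline-negative subjects for induced, baseline-positive for boosted, all evaluable subjects for the combined rate.
- State how a subject with no pre-dose ADA result is handled.

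Align Protocol 7.11 or record the departure in SAP section 8; otherwise the change creates a mismatch between the documents.

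The cost is small. Baseline ADA samples are already scheduled (Protocol Appendix A) and titres are already to be summarized, so no sample or visit is added. The downsides are that the threshold must be justified and the reported incidence may rise. If no subject is boosted, the new line reads zero and settles the question.
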